## 5.0 LIST OF ABBREVIATIONS

Abbreviation or Term a	Definition/Explanation
AE	Adverse event
ALT	Alanine aminotransferase
ANCOVA	Analysis of covariance
ANOVA	Analysis of variance
APTT	Activated partial thromboplastin time
AST	Aspartate aminotransferase
AUC 0-∞	Area under the concentration-time curve from time zero extrapolated to infinite time
AUC 0.6	Area under the concentration-time curve from time zero to 6 hrs post dosing
AV	Atrioventricular
β-HCG	Beta-human chorionic gonadotropin
BID	Twice daily
BLQ	Below limit of quantification
BMI	Body mass index
BP	Blood pressure
BUN	Blood urea nitrogen
Ca ++	Calcium
CBC	Complete blood count
CFR	Code of Federal Regulations
CHF	Congestive heart failure
CI	Confidence interval
Cl 	Chloride
CLcr	Creatinine clearance
C max	Maximum observed concentration
C min	Trough observed concentration
CNS	Central nervous system
CR	Complete response
CRF	Case report form
CSF-1	Colony stimulating factor-1 [also known as macrophage stimulating factor (M-CSF)]
CSF-1R	Colony stimulating factor receptor (also known as Fms)
CTA	Clinical Trial Agreement
CT	Computed tomography
CTCs	Circulating Tumor Cells
CTCAE	Common Toxicity Criteria for Adverse Events
CV	Coefficient of variation
CYP	Cytochrome P450
D/C	Discontinue
ECOG	Eastern Cooperative Oncology Group
eCRF	Electronic case report form
DLT	Dose Limiting Toxicity
ECG	Electrocardiogram

Abbreviation or Terma	Definition/Explanation
ED 50	Effective dose
Eg	Exempli gratia (for example)
ESR	Erythrocyte sedimentation rate
F	Bioavailability
FACS	Fluorescence Activated Cell Sorting
FDA	Food and Drug Administration
GC	Gas chromatography
FDG-PET	Fluorodeoxyglucose (FDG)-positron emission tomography (PET)
GCP	Good Clinical Practice
GFR	Glomerular filtration rate
GGT	Gamma glutamyl transferase
GLP	Good laboratory practice
GVHD	Graft vs. host disease
HBsAg	Hepatitis B surface antigen
HBV	Hepatitis B virus
HCO 3 	Bicarbonate
HCV	Hepatitis C virus
HIV	Human immunodeficiency virus
HNSTD	Highest non-severely toxic dose
HPF	High-power field
HPLC	High-performance liquid chromatography
HR	Heart rate
hr	Hour or hours
IC 50	Half maximal inhibitory concentration
i.e.	Id est (that is)
IEC	Independent ethics committee
IL-1 $\beta$	Interleukin-1 $\beta$
IL-6	Interleukin-6
IL-34	Interleukin-34
INR	International normalized ratio
IRB	Institutional review board
IU	International unit
IV	Intravenous, intravenously
LD 50	Median lethal dose
LDH	Lactate dehydrogenase
LC	Liquid chromatography
LLQ	Lower limit of quantitation
Ln	Natural logarithm
MedRA	Medical Dictionary for Drug Regulatory Activities
MIC	Minimum inhibitory concentration
MMP-3	Matrix metalloproteinase-3
MRI	Magnetic resonance imaging

Abbreviation or Terma	Definition/Explanation
MRSD	Maximum recommended starting dose
MRT	Mean residence time
MS	Mass spectrometry
MTD	Maximum tolerated dose
NOAEL	No-observed-adverse-effect level
NOEL	No-observed-effect-level
PD	Pharmacodynamic(s)
PFS	Progression Free Survival
PK	Pharmacokinetic(s)
PO	Per os (administered by mouth)
PR	Partial response
PT	Prothrombin time
PTT	Partial thromboplastin time
QC	Quality control
RBC	Red blood cell
RT	Radiation therapy
QD	Once daily
QTc	QT interval corrected
QTcF	QT interval corrected using Fredericia equation
SAE	Serious adverse event
SD	Standard deviation or stable disease
STD	Severely toxic dose
STD 10	Severely toxic dose in 10% of animals
T 1/2	Terminal elimination half-life
T3	Triiodothyronine
T4	Thyroxine
T max	Time of maximum observed concentration
TAMs	Tumor-associated macrophages
TEAE	Treatment-emergent adverse event
TID	Three times daily
TMZ	Temozolomide
TSH	Thyroid-stimulating hormone
ULN	Upper limit of normal
ULQ	Upper limit of quantitation
UV	Ultraviolet
V z	Volume of distribution during the terminal phase
V z /F	Apparent volume of distribution during the terminal phase
V ss	Volume of distribution at steady state
WBC	White blood cell
WOCBP	Women of childbearing potential
WONCBP	Women of nonchildbearing potential

a All of these abbreviations may or may not be used in protocol.

**6.0 STUDY SYNOPSIS**

Title	An Open Label Phase 1b/2 Study of Orally Administered PLX3397 in Combination with Radiation Therapy and Temozolomide in Patients With Newly Diagnosed Glioblastoma																																
Study Objective(s)	The study objectives are to assess the potential for PLX3397 to improve the efficacy of standard of care radiation therapy (RT) + temozolomide (TMZ) in patients with newly diagnosed glioblastoma (GBM). For Phase 1b dose escalation, the primary objective is identification of the recommended Phase 2 dose (RP2D). For Phase 2, the primary objective is the comparison of median Progression Free Survival (PFS) to a historical control. Secondary objectives include the evaluation of overall survival (OS), pharmacokinetics (PK), correlative imaging studies, safety, and exploratory endpoints of pharmacodynamic (PD) effects of PLX3397.																																
Study Design	
This will be an open label, uncontrolled Phase 1b/2 trial in patients with newly diagnosed GBM who have recovered from complete or partial surgical resection. All patients will be treated with PLX3397 in addition to standard-of-care combination radiation therapy (RT) plus temozolomide (TMZ) followed by adjuvant TMZ. During Phase 1b dose escalation, two PLX3397 administration schedules, 7 days/week vs. 5 days/week (M-F) will be explored. During Phase 2, patients will be treated with the RP2D.
 
There are 4 sequential periods: 1-week PLX3397 monotherapy; 6-week PLX3397/RT/TMZ combination therapy; 4-week recovery; and, PLX3397/TMZ adjuvant therapy. PLX3397 will be administered twice daily either 7 days/week or 5 days/week (Monday through Friday) starting 1 week prior to the initiation of RT and will continue twice daily either 7 days/week or 5 days/week (Monday through Friday) during the 6-week course of RT.
 
Phase 1b PLX3397 dose and schedule cohorts are:
 
  
 Cohort	Combination PLX3397/RT/TMZ	Adjuvant PLX3397/TMZ	
 
 PLX3397 Dose	PLX3397 Schedule	PLX3397 Dose	PLX3397 Schedule	
   
 -2	600 mg/day	5 days/week (M-F)b	800 mg/dayb	7 days/week	
 
 -1	600 mg/day	7 days/weeka	600 mg/daya 800 mg/dayb	7 days/week	
 
 1	800 mg/day	7 days/weeka 5 days/week (M-F)b	1000 mg/dayb	7 days/week	
 
 2	1000 mg/day	5 days/week (M-F)b	1200 mg/dayb	7 days/week	
  
 
a Amendment 1. b Amendment 2.
 
For combination PLX3397/RT/TMZ PLX3397 treatment, dose escalation to the next highest cohort may occur after all patients have completed the 11-week DLT-observation period (i.e., 1-week PLX3397 monotherapy; 6-week PLX3397/RT/TMZ combination therapy; 4-week recovery). For adjuvant PLX3397/TMZ PLX3397 treatment, dose escalation to the next highest cohort may occur after all patients have completed an 8-week DLT-observation period (i.e., 2 cycles of adjuvant treatment). For patients participating in Phase 1b, intra and inter patient dose escalation to a higher dose level/schedule will be permitted after that dose level/schedule has been established to be safe.
 
The RT schedule will be once 5 days/week (Monday through Friday) for 6 weeks (total radiation dose of 60 Gy using either conformal or IMRT planning). Oral temozolomide will be administered once daily (7 days per week) for the duration of RT. Four weeks after the completion of the course of RT, patients will be started on once-daily adjuvant temozolomide (Day 1-5 of a 28 day cycle) for up to 12 cycles as long as there is no disease progression or unacceptable toxicity and PLX3397 twice daily (28 days of a 28 day cycle) for as long as there is no disease progression or unacceptable toxicity. After discontinuation of study drug, patients will continue to be followed for OS every 6 months.
				Cohort	Combination PLX3397/RT/TMZ		Adjuvant PLX3397/TMZ		PLX3397 Dose	PLX3397 Schedule	PLX3397 Dose	PLX3397 Schedule	-2	600 mg/day	5 days/week (M-F) b	800 mg/day b	7 days/week	-1	600 mg/day	7 days/week a	600 mg/day a 800 mg/day b	7 days/week	1	800 mg/day	7 days/week a 5 days/week (M-F) b	1000 mg/day b	7 days/week	2	1000 mg/day	5 days/week (M-F) b	1200 mg/day b	7 days/week
Cohort	Combination PLX3397/RT/TMZ		Adjuvant PLX3397/TMZ																														
	PLX3397 Dose	PLX3397 Schedule	PLX3397 Dose	PLX3397 Schedule																													
-2	600 mg/day	5 days/week (M-F) b	800 mg/day b	7 days/week																													
-1	600 mg/day	7 days/week a	600 mg/day a 800 mg/day b	7 days/week																													
1	800 mg/day	7 days/week a 5 days/week (M-F) b	1000 mg/day b	7 days/week																													
2	1000 mg/day	5 days/week (M-F) b	1200 mg/day b	7 days/week																													

Number of Patients/Sites	For Phase 1b, 5 cohorts (2 cohorts from Amendment 1 and 3 from Amendment 2) are planned to be enrolled at approximately 7 to 10 sites. Each cohort will consist of approximately 7 patients. Therefore, approximately 35 patients will be enrolled in Phase 1b. Additional patients may be required for replacement patients. Phase 2 will enroll approximately 44 patients.
Study Procedures	
After providing informed consent, patients will undergo screening for eligibility to participate in the study. Screening will start within 3 weeks prior to PLX3397 dosing. Following recovery from surgical resection, patients who meet inclusion/exclusion criteria will start study drug on the morning of any Monday through Friday (Cycle 1 Day 1; C1D1). This visit should occur between 3 weeks and 5 weeks after surgery. Patients will continue to dose study drug twice daily either 7 days/week or 5 days/week (Monday through Friday) and return to the clinic for evaluation on C1D8, the day they initiate radiation therapy plus temozolomide.
 
For the Phase 1b portion of the study, a blood sample will be obtained pre-dose on C1D1 for the baseline PK. On C1D8 and on C1D15, blood samples will be obtained pre-dose and 1, 2, 4, and 6 hours post-dose to estimate PLX3397 PK. Patients will return to the clinic on Cycle 2 Day 1 (C2D1) for evaluation. If PLX3397 has been well tolerated and there has been no clinical evidence of disease progression, continued dosing will be permitted. Patients will be monitored for response and disease progression with MRI brain scans every 2 cycles, with the brain scan obtained approximately 3-4 weeks after the completion of RT serving as the baseline scan for determination of progression.
 
For Phase 1b PLX3397 dose and schedule cohorts and escalation, see Study Design (above.)
 
For the Phase 2 portion of the study, patients will be treated with PLX3397 at the RP2D level.
 
For both phases, patients will be monitored throughout the study for adverse reactions to the study drug and/or study procedures.
 
Hematology assessments (i.e., CBC, differential count, and platelet count) will be performed weekly starting with C1D1 and continuing through the first week of the Recovery Period (RPD8). Serum chemistry assessments will be performed at Screening, C1D1, C1D15, C2D1, and C2D22 (completion of RT). For the adjuvant treatment period, assessments will be made on the day of treatment initiation (C3D1), C3D22, and D22 of each subsequent cycle, and at study completion or upon early withdrawal. A serum pregnancy test will be completed at Screening for applicable patients.
 
Blood pressure, respiratory rate, pulse rate and temperature will be measured at each study visit. A standard 12-lead electrocardiogram (ECG) will be performed for each patient at Screening, C1D1, C2D1, and study completion.
 
A complete physical examination will be performed for each patient at Screening. A neurological exam and a symptom-directed physical exam will be completed on each subsequent visit while continuing study therapy, and at study completion or upon early withdrawal. Patients will also complete the MD Anderson Symptom Inventory-Brain Tumor Module at the time points noted in the Trial Flow Chart, and Karnofsky performance status will be recorded as noted.
 
A surgical paraffin tumor block (or at least 20 unstained slides) will be identified during Screening for subsequent shipment to the central pathologist. Blood samples for circulating CSF-1, biomarkers of kinase inhibition and myeloid cell recruitment will be obtained pre-dose on C1D1, C1D8, C2D1, and C3D1. CD14/16 mononuclear cell counts will be obtained pre-dose on C1D1 and C1D8.
 
Commencing on 01 October 2017, patient visits, clinical laboratory testing, and MRI brain scans will be performed approximately every 12 weeks (please refer to the TRIAL FLOW CHART – Phase 2 for details).



Key Patient Selection Criteria
	
Inclusion
 
 
1. Male or female patients <math>\geq 18</math> years old.
 
2. Histologically confirmed definitive GBM or gliosarcoma by partial or complete surgical resection (i.e. not by biopsy only) within 5 weeks prior to PLX3397 administration (C1D1). Tumor must have a supratentorial component. For all patients, availability of a surgical paraffin tumor block sufficient to generate at least 20 unstained slides; or, if a paraffin tumor block is unavailable, at least 20 unstained slides.
 
3. The patient must have recovered from the effects of surgery, post-operative infection, and other complications before study registration.
 
4. A diagnostic contrast-enhanced MRI or CT scan of the brain must be performed preoperatively and postoperatively prior to the initiation of radiotherapy, within 28 days (preferably 14 days) prior to C1D1.
 
5. Patients unable to undergo MR imaging because of non-compatible devices can be enrolled, provided pre- and post-operative contrast-enhanced CT scans are obtained and are of sufficient quality.
 
6. Patients must receive RT at the participating institution.
 
7. Women of child-bearing potential must have a negative pregnancy test within 14 days of initiation of dosing and must agree to use an acceptable method of birth control while on study drug and for 3 months after the last dose. Women of non-childbearing potential may be included if they are either surgically sterile or have been postmenopausal for <math>\geq 1</math> year. Men of child-bearing potential must also agree to use an acceptable method of birth control while on study drug, and for 3 months after the last dose.
 
8. Karnofsky performance status of <math>\geq 70</math>.
 
9. Adequate hematologic, hepatic, and renal function (absolute neutrophil count <math>\geq 1.5 \times 10^9/L</math>, Hgb <math>> 10</math> g/dL, platelet count <math>\geq 100 \times 10^9/L</math>, AST/ALT <math>\leq 2.5 \times</math> ULN, creatinine <math>\leq 1.5 \times</math> ULN).
 
10. Willing and able to provide written informed consent prior to any study related procedures and to comply with all study requirements.
 
 
Exclusion
 
 
1. Evidence of recurrent GBM or metastases detected outside of the cranial vault.
 
2. Investigational drug use within 28 days of the first dose of PLX3397 or concurrently.
 
3. Prior use of Gliadel wafers or any other intratumoral or intracavitary treatment.
 
4. Prior radiation or chemotherapy for glioblastoma or glioma.
 
5. Prior chemotherapy or radiosensitizers for cancer of the head and neck (except for T1 glottic cancer) that would result in an overlap of radiation fields.
 
6. Prior allergic reaction to temozolomide.
 
7. History of Grade 2 (CTCAE v4) or greater acute intracranial hemorrhage.
 
8. Active cancer (either concurrent or within the last 3 years) that requires non-surgical therapy (e.g. chemotherapy or radiation therapy), with the exception of surgically treated basal or squamous cell carcinoma of the skin, melanoma in-situ, or carcinoma in-situ of the cervix.
 
9. Chronic active hepatitis B or C.
 
10. Refractory nausea and vomiting, malabsorption, biliary shunt, or significant bowel resection that would preclude adequate absorption of study drug.
 
11. Patients with serious illnesses, uncontrolled infection, medical conditions, or other medical history including abnormal laboratory results, which in the investigator's opinion would be likely to interfere with a patient's participation in the study, or with the interpretation of the results.
 

--	--

	
12. Women of child-bearing potential who are pregnant or breast feeding.
 
13. At Screening QTcF <math>\geq 450</math> msec for males and <math>\geq 470</math> msec for females.

Dosage and Regimen	
Study drug will be administered orally using a capsule formulation (200 mg per capsule). The total daily dose of PLX3397 will be divided and administered BID. For an uneven number of capsules, the larger dose will be administered in the morning.
 
For Phase 1b PLX3397 dose and schedule cohorts and escalation, see Study Design (above).
 
The Phase 2 portion of the study will use the RP2D selected from the Phase 1b portion of the study.
 
As a part of standard of care, patients will receive the following:
 
 
• 60 Gy of radiation therapy Monday-Friday for a total of 30 radiation treatments over approximately 6 weeks.
 
• Temozolomide 75 mg/m^2 PO once daily for approximately 6 weeks beginning the first day of RT until RT end, followed by adjuvant treatment at a dose of 150 mg/m^2 once daily on Days 1-5 of the first 28 day cycle after completion of radiation therapy (start of Cycle 3). The dose can be escalated to 200 mg/m^2 if the non-hematologic toxicity is Grade <math>\leq 2</math> (except for alopecia, nausea, and vomiting), absolute neutrophil count (ANC) is <math>\geq 1.5 \times 10^9/L</math>, and the platelet count is <math>\geq 100 \times 10^9/L</math>.
 
• During the 4-week break after the completion of RT, neither temozolamide nor study drug will be administered.
 

Safety and Tolerability Assessments	
Physical examinations, vital signs, 12-lead ECGs, adverse events, hematology, and serum chemistry will be used to assess safety and tolerability.
 
As this is an open label study, ongoing safety will be continuously and rigorously monitored by the Sponsor. Additionally, biweekly teleconferences are planned to review in detail the safety across all study sites. Prior to dose escalation in the Phase 1b portion, safety data will be collated and reviewed by the Sponsor and study sites by teleconference.

Dose Limiting Toxicities (Phase 1b)	
Using CTCAEv4 grading criteria:
 
Hematologic DLTs
 
 
• Grade <math>\geq 3</math> febrile neutropenia
 
• Grade 4 neutropenia lasting for <math>>7</math> days (growth factors allowed)
 
• Grade 3 thrombocytopenia (platelets <math>\leq 50.0/\mu L</math>) lasting for <math>>7</math> days
 
 
Grade 3-4 lymphopenia is NOT considered a DLT.
 
Non-hematologic DLTs
 
 
• Any Grade <math>\geq 3</math> non-hematologic toxicity, probably related to study drug, EXCEPT for the following: 
 
• Grade <math>\geq 3</math> neurologic deficits considered to be due to the effects of tumor, resection, or expected post-surgical morbidities
 
• Seizures of any grade, as this is commonly observed in this patient population
 
• Grade <math>\geq 3</math> thromboembolic event, as this is commonly observed in this patient population
 
• Grade 3 nausea, vomiting, or diarrhea that resolves to Grade <math>\leq 2</math> within 3 days of onset
 
• Grade 3 headache, insomnia, or amnesia that resolves to Grade <math>\leq 2</math> within 14 days of onset
 
• Grade 3 fatigue that resolves to <math>\leq</math> Grade 2 within 21 days of onset
 
• Grade 3 AST or ALT that resolves to <math>\leq</math> Grade 2 within 21 days of onset
 
• Grade <math>\geq 3</math> CPK, GGT, ALP, hypomagnesemia, or hypophosphatemia that is felt by the investigator to be clinically insignificant
 
 
 

	
 
• Alopecia of any Grade
 

Stopping Rules	
For Phase 1 dose escalation, a dose level will be considered unacceptable if 2 or more patients of the 6 eligible patients experience a DLT (see below). Should all 7 patients in the Cohort be analyzable for adverse events, only the first 6 will be considered in the determination of DLTs. A patient who misses more than 7 days of PLX3397 administration during the 7-week dosing period of Cycle 1 (4 weeks) and Cycle 2 (3 weeks) for reasons other than having had a DLT will be replaced. If 2 or more patients in a Cohort experience a DLT, no patients in the Cohort will be replaced. If >2 of the first 6 patients in Dose Level -2 (400 mg/day of PLX3397) experience a protocol-defined DLT, the combination will be considered too toxic and the study will be discontinued.
 
After approximately 50% of the planned Phase 2 patients have completed their concurrent radiation therapy, an overall interim safety summary will be reviewed by the Medical Monitor and principal investigators to ensure that the potential clinical benefit outweighs the observed clinical risk to date. If the safety observations do not warrant continued enrolment, the study will be discontinued.

PK Parameters	For the Phase 1b portion of the study, a partial AUC ( $AUC_{0-6}$ ) will be calculated using samples collected from C1D8 (pre-temozolomide) and C1D15 (concurrent temozolomide). Values for $C_{max}$ and $T_{max}$ will be determined from the concentration-time profile.
PD Parameters	CD14/16 mononuclear cell counts, CSF-1, and biomarkers of kinase inhibition and myeloid cell recruitment. Surgical tissue will be evaluated for MGMT methylation, CSF-1, CSF1R, tumor-associated macrophages, and other prognostic biomarkers in order to correlate with treatment response and inform enrichment strategies for subsequent studies in this patient population. If the MGMT methylation status of the study population differs from that observed in the RTOG 0525 study, the benchmark mPFS of 5.5 months will be adjusted appropriately.
Endpoints	
Primary: Median PFS by RANO criteria
 
Secondary: Safety, OS, PK, correlative imaging
 
Exploratory: PD biomarkers

Statistical Considerations	For the primary endpoint of median PFS, based on a one-sided log rank test with a significance level of 0.1 and power of 80%, 22 events (death or progression) in approximately 31 patients would be required to detect a 50% relative hazard reduction in progression-free survival due to the addition of PLX3397 compared to the recent historical control median PFS of 5.5 months (RTOG 0525). Assuming a ~ 30% rate of non-evaluability, approximately 37 patients are planned to be enrolled in the Phase 2 portion of the study, which when combined with the 7 patients treated at that dose level in the Phase 1 portion of the study will yield approximately 44 patients.

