**TRIAL FLOW CHART – Phase 1b Dose Escalation Phase**

STUDY DAY▶	Screening	4 Week Cycle				3 Week Cycle				4 Week Recovery Period				4 Week Cycle		4 Week Cycle	End of Rx
	Day -21 to -1	C1D1 (-2d)	C1D8 ±2d	C1D15 ±2d	C1D22 ±2d	C2D1 ±2d	C2D8 ±2d	C2D15 ±2d	C2D22  ±2d	RPD 1 ±2d	RPD 8 ±2d	RPD 15 ±2d	RPD 22 ±2d	C3D1  ±7d	C3D22 ±2d	Day 22 of Cycle 4+  ± 7d	
EVENT ▼																	
Informed Consent	X																
Medical History	X																
Height	X																
Weight	X	X				X			X					X	X	X	X
Vital Signs	X	X	X	X		X			X					X	X	X	X
Physical Exam 	X	X	X	X		X			X					X	X	X	X
ECG 	X					X											X
Chem	X	X		X		X			X					X	X	X	X
Hematology 	X	X	X	X	X	X	X	X	X		X			X	X	X	X
Plasma for PK 		X	X	X													
Plasma PD Biomarkers 		X	X			X								X			
Whole Blood for CD14/16		X	X														
Serum Pregnancy Test 	X																X
Surgical Specimen for PD	X																
Karnofsky Performance Status	X	X				X			X					X	X	X	X
MDA Symptom Inventory		X							X					X	X	X	X
MRI Brain Scan 	X													X		X	
Study Drug Dosing 		X-----X												X-----X			
Study Drug Compliance		X	X	X		X			X						X	X	X
Radiation Therapy			X-----X														
Temozolomide 			X-----X												X 		
Concomitant Medications	X	X	X	X		X			X					X	X	X	X
Adverse Events 		X	X	X		X			X					X	X	X	X

EXPLANATION OF SUPERSCRIPTS:

1. The cycle length for Cycle 2 is 3 weeks, to complete the 6 weeks total of radiation therapy.
2. C3D1 is the first dose of the adjuvant retreatment with temozolomide and study drug, beginning approximately 4 weeks after the completion of RT.
3. If well tolerated and no tumor progression; clinic visits, laboratories every 4 weeks with radiographic assessment performed every 8 weeks (every 2 cycles).
4. Complete physical exam (including neurological exam) at Screening, and neurological exam plus symptom-directed physical exam subsequently.
5. Hematology: CBC, differential count, platelet count.
6. On C1D1, obtained pre-dose. On C1D8 and C1D15, obtained pre-dose, 1, 2, 4, and 6 hours post-dose.

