### **13.6 Cycle 2 Day 22 ( $\pm 2$ Days), [3 week cycle]**

On C2D22, all patients will return to the clinic and undergo the following procedures:

1. Weight, vital signs, neurological exam plus symptom-directed physical examination.
2. Clinical laboratory evaluation (hematology and serum chemistry).
3. Karnofsky performance status assessment.
4. MDA Symptom Inventory.
5. Study drug compliance.

6. Recording of concomitant medications.
7. AE monitoring.
8. Instruct patient to obtain RPD8 ( $\pm 2$  days) hematology evaluation (CBC, differential count, platelet count) either at study site or local laboratory.

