### **13.7 Day 1 of Cycle 3 ( $\pm 7$ Days), [4 week cycle]**

Following a 4 week recovery period, all patients will return to the clinic on C3D1 and undergo the following procedures:

1. Weight, vital signs, neurological exam plus symptom-directed physical examination.
2. Clinical laboratory evaluation (hematology and serum chemistry).
3. Pre-dose blood sample collection for PD response biomarkers.
4. Karnofsky performance status assessment.
5. MDA Symptom Inventory.
6. MRI brain scan to be obtained at the end of each even-numbered cycle.
7. Re-initiation of study drug dosing 7 days/week.
8. Initiation of temezolomide adjuvant therapy. Temozolomide is taken orally once daily for 5 days followed by 23 days without treatment for each cycle beginning with C3D1.
9. Recording of concomitant medications.
10. AE monitoring.

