**Table 2: PLX3397 Dosing Cohorts**

Cohort	Combination PLX3397/RT/TMZ		Adjuvant PLX3397/TMZ	
	PLX3397 Dose	PLX3397 Schedule	PLX3397 Dose	PLX3397 Schedule
-2	600 mg/day	5 days/week (M-F) b	800 mg/day b	7 days/week
-1	600 mg/day	7 days/week a	600 mg/day a 800 mg/day b	7 days/week
1	800 mg/day	7 days/week a 5 days/week (M-F) b	1000 mg/day b	7 days/week
2	1000 mg/day	5 days/week (M-F) b	1200 mg/day b	7 days/week

a Amendment 1.

b Amendment 2.

Study drug will be administered orally using a capsule formulation (200 mg per capsule). The total daily dose of PLX3397 will be divided and administered BID. For an uneven number of capsules, the larger dose will be administered in the morning.

For combination PLX3397/RT/TMZ PLX3397 treatment, dose escalation to the next highest cohort may occur after all patients have completed the 11-week DLT-observation period (i.e., 1-week PLX3397 monotherapy; 6-week PLX3397/RT/TMZ combination therapy; 4-week recovery). For adjuvant PLX3397/TMZ PLX3397 treatment, dose escalation to the next highest cohort may occur after all patients have completed an 8-week DLT-observation period (i.e.,

2 cycles of adjuvant treatment). For patients participating in Phase 1b, intra and inter patient dose escalation to a higher dose level/schedule will be permitted after that dose level/schedule has been established to be safe.

Prior to dose escalation, safety data will be collated and reviewed by the Sponsor and study sites by teleconference. A dose level will be considered unacceptable if 2 or more patients of the 6 eligible patients experience a DLT (see below). Should all 7 patients in the Cohort be analyzable for adverse events, only the first 6 will be considered in the determination of DLTs. A patient who misses more than 7 days of PLX3397 administration during the 7-week dosing period of Cycle 1 (4 weeks) and Cycle 2 (3 weeks) for reasons other than having had a DLT will be replaced. If 2 or more patients in a Cohort experience a DLT, no patients in the Cohort will be replaced.

If 2 or more of the first 6 patients in Cohort -2 (600 mg/day of PLX3397; 5 days/week [M-F]) experience a protocol-defined DLT, the combination will be considered too toxic and the study will be discontinued.

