### 13.13.2 Dose-Limiting Toxicities

Dose-limiting toxicities will be assessed using CTCAEv4 grading criteria. During the Phase 1b portion of the study, the DLT window will consist of 11 weeks (1 week PLX3397 run-in, 6 weeks of PLX3397 in combination with RT/temozolomide, and 4 weeks of post-RT recovery). The following will be considered DLTs:

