#### Hematologic DLTs

- Grade  $\geq 3$  febrile neutropenia
- Grade 4 neutropenia lasting for  $>7$  days (growth factor support allowed)
- Grade 3 thrombocytopenia (platelets  $\leq 50.0/\mu\text{L}$ ) lasting for  $>7$  days

Grade 3-4 lymphopenia is NOT considered a DLT.

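### Phase 1b schedules no blood count between RPD8 and C3D1, a 21-day stretch of the 77-day DLT window, so a cytopenia that meets the DLT definition can go unseen; the likely effect is small and the remedy cheap

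*Combined protocol and SAP*

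**What the plan says.** **Definition.** Section 13.13.2 states that "the DLT window will consist of 11 weeks": 1 of run-in, 6 of combination therapy and 4 of post-radiotherapy recovery. Among the hematologic DLTs is "Grade 4 neutropenia lasting for" more than 7 days; Grade 3 thrombocytopenia carries the same duration condition. Lymphopenia is excluded.

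**Counts up to C3D1.** In the synopsis (Study Procedures), hematology "will be performed weekly starting with C1D1 and continuing through the first week of the Recovery Period (RPD8". Section 13.6 agrees, its only recovery-period item being "Instruct patient to obtain RPD8" hematology, at the study site or a local laboratory. Section 13.7 then says "Following a 4 week recovery period, all patients will return to the clinic on C3D1". The Phase 1b flow chart has RPD15 and RPD22 columns, but hematology is marked in neither. Section 18.4 makes the flow chart govern laboratory tests.

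**Adjuvant period.** Section 13.13.1 says escalation of the adjuvant dose "may occur after all patients have completed an 8-week DLT-observation period", meaning Cycles 3 and 4. In the synopsis, "assessments will be made on the day of treatment initiation (C3D1), C3D22, and D22 of each subsequent cycle". Section 13.9 agrees, and flow-chart footnote 3 has "clinic visits, laboratories every 4 weeks". No C4D1 count is scheduled. The temozolomide label in Attachment 4 (5.4) asks for a count on Day 1 and Day 22 of each 28-day cycle.

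**The concern.** A duration-based DLT can be scored only if counts are taken often enough to see the episode. The plan samples weekly for the first eight weeks, then stops while the DLT window is still open. A site that follows the schedule exactly can therefore record no DLT in a patient who had one, because the episode began and resolved between RPD8 and C3D1. Febrile neutropenia would present clinically; an asymptomatic fall in neutrophils or platelets would not.

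DLT counts among six patients decide escalation and feed the recommended Phase 2 dose. With two DLTs making a dose unacceptable, one missed event can change the decision for an individual cohort. An unseen low count is also a direct safety matter for the patient.

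**Working it through.** **1. Calendar (flow chart, synopsis).** Cycle 1 is days 1-28, Cycle 2 days 29-49, recovery days 50-77. The plan's window reproduces: (1 + 6 + 4) × 7 = 77 days. Scheduled counts fall on days 1, 8, 15, 22, 29, 36, 43, 50 and 57 (RPD8), then 78 (C3D1). Every interval is 7 days except the last: 78 − 57 = 21 days, and 21/77 = 27% of the window. With RPD8 ±2 and C3D1 ±7 days, the gap runs from 71 − 59 = 12 to 85 − 55 = 30 days.

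**2. Chance that an episode starting in the gap is unseen.** Assume onset is even over a gap of G days and the patient stays at DLT grade for D days. No scheduled count falls inside the episode if it starts in the first G − D days, so P(unseen) = 1 − D/G, or 0 if D ≥ G.

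| D (days) | G = 21 | G = 12 | G = 30 |
|---|---|---|---|
| 8 | 62% | 33% | 73% |
| 10 | 52% | 17% | 67% |
| 14 | 33% | 0% | 53% |

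Averaged over the visit windows the figures are 60%, 50% and 30%.

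**3. With RPD15 (day 64) and RPD22 (day 71) added.** The longest nominal interval becomes 7 days, so no episode of 8 days or more can fall between counts held on their nominal days. Simulation with whole-day visit windows (±2 for the recovery counts, ±7 for C3D1), and onset even between the actual RPD8 and C3D1 visits, leaves about 9%, 3% and 0.2% unseen for D = 8, 10 and 14.

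**4. Effect on the dose decision.** Section 13.13.1 accepts a dose if at most 1 of 6 patients has a DLT. Assumptions, none of them from the documents: true DLT rate 30%; onset even over 77 days; a fraction f of DLTs are prolonged cytopenias lasting 8 to 14 days (mean 11). The chance that such a DLT is unseen is u = (1 − 11/21) × 21/77 = 10/77 = 0.130. The observed rate is 0.30 × (1 − f × u), and acceptance is P(X ≤ 1) for a binomial with n = 6.

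| f | Observed DLT rate | Acceptance |
|---|---|---|
| 0 | 0.300 | 0.420 |
| 0.10 | 0.296 | 0.429 |
| 0.25 | 0.290 | 0.441 |
| 0.50 | 0.281 | 0.463 |

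Section 21.1.1 words the rule differently (no more than 2 of 6). Under that wording, f = 0, 0.10 and 0.25 give 0.744, 0.751 and 0.762. The shift is equally small.

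**5. Adjuvant period, calendar only.** Counting from C3D1 as day 1, the scheduled counts are days 1, 22 and 50, so the intervals are 21 and 28 days. A C4D1 count on day 29 splits the 28 days into 7 + 21. Intervals of 21 days then remain before C3D22 and before C4D22.

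**The case against.** **No study treatment is given in the gap.** The synopsis and section 16.1 stop both temozolomide and PLX3397 for these four weeks, and radiotherapy is over. The documents give no cytopenia rate for the period. This stands: the percentages in step 2 are conditional on an episode starting in the gap, and the expected number of missed DLTs cannot be computed. It does not remove the mismatch, because the protocol itself counts these weeks as DLT observation.

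**The decision barely moves.** This also stands, and it fixes the severity. A reader might infer that the gap makes the escalation decisions or the recommended Phase 2 dose unreliable. The documents do not support that: the average change in acceptance is one to two percentage points under the assumptions above.

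**The schedule is a minimum.** Section 18.0 allows more frequent safety evaluations, and RPD8 already goes beyond the label, whose count rules cover the radiotherapy phase and the 28-day cycles but not the break. That softens the point only in part, since an asymptomatic patient gives no prompt for an extra test.

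**The adjuvant gap is largely covered by the label.** A reader might note that the label (6.1) puts median nadirs at 26 days for platelets and 28 for neutrophils, between C3D22 and C4D22, and infer that most adjuvant cytopenias would be missed. The documents do not support that either. Label sections 2.1, 5.1 and 5.4 already require or ask for counts when each temozolomide cycle starts. Weekly repeats apply while ANC is below 1.5 or platelets below 100 × 10⁹/L, which is well above DLT grade, so a Day 22 value on the way down can trigger them. The nadir figures come from an anaplastic astrocytoma study without PLX3397 and are only medians and ranges. Any percentage unseen would depend mainly on the distribution chosen and on how early the repeat trigger is crossed, so none is given here.

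**Conclusion.** The concern holds for the recovery period, as a low-severity point. The synopsis, the flow chart and sections 13.6 and 13.7 agree that no count is scheduled between RPD8 and C3D1, while section 13.13.2 keeps those weeks in the DLT window and defines two DLTs by duration. The calendar finding needs no assumption. The 62%, 52% and 33% rest on even onset over a nominal 21-day gap. The acceptance shift of about 0.42 to 0.43-0.44 rests on the assumed 30% DLT rate, even onset over the window, and 10-25% of DLTs being prolonged cytopenias.

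The adjuvant part is secondary. The flow chart omits a Day 1 count that the attached label asks for inside the 8-week observation period. The change there aligns the two documents; it is not evidence of a large detection failure.

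**What to change.** **Main change.** In the Phase 1b flow chart, the synopsis (Study Procedures) and section 13.6, add hematology at RPD15 and RPD22 (±2 days), at the study site or a local laboratory as already allowed for RPD8. Extend the label's weekly-until-recovery repeat rule to the recovery period.

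**Secondary change.** Add a pre-dose C4D1 count to the Phase 1b flow chart, the synopsis and section 13, matching label 5.4. This narrows the adjuvant gaps but does not close them.

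**Cost.** Two recovery counts plus C4D1 make three routine blood counts per Phase 1b patient: 3 × 7 = 21 per cohort and 3 × 35 = 105 for the planned 35 patients. No extra clinic visit is needed if a local laboratory is used. Weekly counts still date an episode only to within about a week, so durations close to 7 days will remain uncertain.
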